### 9.6.2 Statistical Methods for Safety Analyses

All safety summaries and analyses will consider the cohorts separately (i.e., treatment groups will not be pooled across cohorts).

Safety and tolerability will be assessed by clinical review of all relevant parameters including adverse events (AEs), laboratory tests and vital signs.

The analysis of safety results will follow a tiered approach (Table 7). The tiers differ with respect to the analyses that will be performed. Safety parameters or adverse events of special interest that are identified a priori constitute "Tier 1" safety endpoints that will be participant to inferential testing for statistical significance with p values and 95% confidence intervals provided for between-group comparisons. Nominal p-values will be provided without any adjustments to account for multiple comparisons. Other safety parameters will be considered Tier 2 or Tier 3. Tier 2 parameters will be assessed via point estimates with 95% confidence intervals provided for between-group comparisons; only point estimates by treatment group are provided for Tier 3 safety parameters.

Adverse events (specific terms as well as system organ class terms) and predefined limits of change in laboratory test and vital signs parameters that are not pre-specified as Tier-1 endpoints will be classified as belonging to "Tier 2" or "Tier 3", based on the number of events observed. Membership in Tier 2 requires that at least 4 participants in any treatment group exhibit the event; all other adverse events and predefined limits of change will belong to Tier 3.

The threshold of at least 4 events was chosen because the 95% confidence interval for the between-group difference in percent incidence will always include zero when treatment groups of equal size each have less than 4 events and thus would add little to the interpretation of potentially meaningful differences. Because many 95% confidence intervals may be provided without adjustment for multiplicity, the confidence intervals should be regarded as a helpful descriptive measure to be used in review, not a formal method for assessing the statistical significance of the between-group differences in adverse events and predefined limits of change.

Continuous measures such as changes from baseline in laboratory test and vital signs parameters that are not pre-specified as Tier-1 endpoints will be considered Tier 3 safety parameters.

Summary statistics for baseline, on-treatment, and change from baseline values will be provided by treatment group in table format.

For this protocol, the specific Tier 1 adverse events are listed in [Table 7](#). In addition, summary measures of AEs consisting of the percentage of participants with any AE, a drug related AE, a serious AE, an AE which is both drug-related and serious, and who discontinued due to an AE, who discontinued due to a drug-related AE, who discontinued due to a serious AE and who discontinued due to a drug-related and serious AE will be considered Tier 2 endpoints. P-values (Tier 1 only) and 95% confidence intervals (Tier 1 and Tier 2) will be provided for between-treatment differences in the percentage of participants with events; these analyses will be performed using the Miettinen and Nurminen method (1985), an unconditional, asymptotic method [Miettinen, Olli and Nurminen, Markku 1985].

Table 7 Analysis Strategy for Safety Parameters

Safety Tier	Safety Endpoint	p-Value	95% CI for Treatment Comparison	Descriptive Statistics
Tier 1	Hepatitis-related AEs	X	X	X
	Consecutive elevations in ALT $\geq 3$ xULN	X	X	X
	Consecutive elevations in AST $\geq 3$ xULN	X	X	X
	Consecutive elevations in ALT $\geq 3$ xULN or consecutive elevations in AST $\geq 3$ xULN	X	X	X
	ALT elevation $\geq 5$ xULN	X	X	X
	AST elevation $\geq 5$ xULN	X	X	X
	ALT elevation $\geq 5$ xULN or AST elevation $\geq 5$ xULN	X	X	X
	Potential Hy's Law Condition (ALT or AST elevations $>3$ xULN, with ALP $<2$ xULN and TBL $\geq 2$ xULN)	X	X	X
	Elevations in CK $\geq 5$ xULN with muscle symptoms	X	X	X
	Elevations in CK $\geq 10$ xULN	X	X	X
	Elevations in CK $\geq 10$ xULN with muscle symptoms	X	X	X
	Elevations in CK $\geq 10$ xULN with muscle symptoms that are considered drug-related	X	X	X
Tier 2	Any AE		X	X
	Any Serious AE		X	X
	Any Drug-Related AE		X	X
	Any Serious and Drug-Related AE		X	X
	Discontinuation due to AE		X	X
	Discontinuation due to drug-related AE		X	X
	Discontinuation due to serious AE		X	X
	Discontinuation due to serious and drug-related		X	X
	Specific AEs, SOCs (incidence $\geq 4$ of participants in all of the treatment groups)		X	X
Tier 3	Specific AEs, SOCs (incidence $<4$ of participants in all of the treatment groups)			X
	Change from baseline in laboratory tests and vital signs			X
SOC=System Organ Class; X = results will be provided.				

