#### 4.2.1.2 Safety Endpoints

The safety will be evaluated with clinical and laboratory safety assessments conducted throughout the trial. Centralized liver function test and other biochemistry test will be done at Visit 3, Visit 5 and Visit 6 to detect potential hepatic adverse events and muscle adverse events which were defined as AE of interest. The rational of arrangement is based on the facts as follow. Atorvastatin and Ezetimibe, as the active ingredients, have been authorized and widely used in China as well as worldwide for many years with well-established safety profile. A consistent safety profile is expected of this FDC. According to the label of atorvastatin, the majority of liver function abnormality occurs in first 3 months post the 1st dose, liver function test is suggested to be performed prior to initiation and at 3 month as a standard recommendation according to the label. Atorvastatin, like other statins, occasionally provoke myopathy and rhabdomyolysis, especially concomitant use with cyclosporine or potent CYP3A4 inhibitors like clarithromycin. However, surveillance of creatine kinase (CK) cannot prevent the occurrence of myopathy or rhabdomyolysis. Regular surveillance of CK is only recommended when those drugs mentioned above are prescribed for concomitant use as recommended in the label. Ezetimibe was generally well tolerated and when given as concomitant use with statin physicians should refer to the directions for use of statin according to the ezetimibe label. In addition, unnecessary blood test cause participant's burden and can potentially cause the procedure related adverse event, e.g. injection site reaction and negative impact on the willingness of participation.

In addition to the centralized lab test according to the scheduled visits, qualifying local lab can be used to evaluate the eligibility during the screening and also to detect the safety signal during the trial conduction when needed.

Clinical measurements include monitoring of vital signs/physical examination at each visit will be done. Tiered methods will be used for safety endpoints analysis according to severity, frequency and relationship with the drug.

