## **8.3 Safety Assessments**

The assessment of safety will be based primarily on the frequency of AEs, SAEs, and laboratory abnormalities. Other safety data will be summarized as appropriate.

1. Laboratory evaluations (performed at baseline and at the end of the study)
2. Adverse events and serious adverse events, adverse events of interest including muscular event and hepatic events (performed throughout full study)
3. Discontinuation due to AEs (performed throughout full study)
4. Physical Exam (performed throughout full study)
5. Vital signs (performed throughout full study)

Details regarding specific safety procedures/assessments to be performed in this study are provided. The total amount of blood/tissue to be drawn/collected over the course of the study (from prestudy to poststudy visits), including approximate blood/tissue volumes drawn/collected by visit and by sample type per participant, can be found in Section 8.

Planned time points for all safety assessments are provided in the SoA.

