#### **8.4.7 Events of Clinical Interest (ECIs)**

Selected nonserious and SAEs are also known as ECIs and must be reported to the Sponsor.

Events of clinical interest for this study include:

1. An elevated AST or ALT lab value that is greater than or equal to 3X the upper limit of normal and an elevated total bilirubin lab value that is greater than or equal to 2X the upper limit of normal and, at the same time, an alkaline phosphatase lab value that is less than 2X the upper limit of normal, as determined by way of protocol-specified laboratory testing or unscheduled laboratory testing.\*

\*Note: These criteria are based upon available regulatory guidance documents. The purpose of the criteria is to specify a threshold of abnormal hepatic tests that may require an additional evaluation for an underlying etiology. The study site guidance for assessment and follow-up of these criteria can be found in the Investigator Study File Binder (or equivalent).

2. An overdose of Sponsor's product, as defined in Section 8.5, that is not associated with clinical symptoms or abnormal laboratory results.
3. Myopathy, rhabdomyolysis, or if the CK criterion necessitating study medication discontinuation is met, the event should be reported as ECI because of their association with lipid-lowering treatments.

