## 9.1 Statistical Analysis Plan Summary

Key elements of the statistical analysis plan are summarized below; the comprehensive plan is provided in Sections 9.2-9.12.

Study Design Overview	A Phase III, Randomized, Double-blind Clinical Trial to Study the Efficacy and Safety of MK-0653C in Chinese participants with Hypercholesterolemia
Treatment Assignment	A double-blind/masking technique will be used. After the run-in period, 180 participants will be randomized in a ratio of 1:1 into the arms of MK-0653C 10/10 mg and atorvastatin 20 mg in Cohort A and 270 participants will be randomized in a ratio of 1:1 into the arms of MK-0653C 10/20 mg and atorvastatin 40 mg in Cohort B. Randomization will be stratified by disease risk category (low, moderate, high, very high) as defined in Section 4.1.
Analysis Populations	Efficacy: Full Analysis Set (FAS) Safety: All Participants as Treated (APaT)
Primary Endpoint	Percent change from baseline in LDL-C at Week 12
Secondary Endpoints	1. Percentage of participants with adverse events. 2. Change from baseline in laboratory parameters and vital signs at each visit 3. Percentage of participants discontinued from study medication
Statistical Methods for Key Efficacy Analyses	The primary hypothesis for each cohort will be evaluated by comparing MK-0653C to atorvastatin on the percent change from baseline in LDL-C using a constrained longitudinal data analysis (cLDA) model.
Statistical Methods for Key Safety Analyses	Counts and percentages of AEs will be provided. P-values and confidence intervals for the incidence of AEs of clinical interest will be estimated using the Miettinen and Nurminen method [Miettinen, Olli and Nurminen, Markku 1985].
Interim Analyses	No interim analyses are planned for this trial.
Multiplicity	The Type-I error rate over the multiple treatment comparisons will be controlled by the Hochberg testing procedure.
Sample Size and Power	A total of approximately 450 participants (180 in Cohort A, 270 in Cohort B) will be randomized. The sample in Cohort A has 93% power to demonstrate the superiority of MK-0653C 10/10 mg over atorvastatin 20 mg at a one-sided 2.5% alpha-level. Similarly, the sample in Cohort B has 95% power to demonstrate the superiority of MK-0653C 10/20 mg over atorvastatin 40 mg at a one-sided 2.5% alpha-level. The overall power to succeed on at least one hypothesis is 99% at a 2.5% alpha-level with 88% power to succeed for both hypotheses.

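### All four Tier 1 muscle rows in Table 7 require a CK elevation, so a myopathy or muscle-symptom AE with CK below 5xULN, or with no concurrent CK, gets no Tier 1 comparison

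*Combined protocol and SAP*

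**What the plan says.** - **Events of interest.** Section 4.2.1.2 says central biochemistry is done "to detect potential hepatic adverse events and muscle adverse events which were defined as AE of interest". Section 8.3 lists "adverse events of interest including muscular event and hepatic events" among the safety assessments.
- **Events of clinical interest.** The third item in Section 8.4.7 reads "Myopathy, rhabdomyolysis, or if the CK criterion necessitating study medication discontinuation is met". Myopathy and rhabdomyolysis stand there as alternatives to the CK criterion, not as consequences of it.
- **Rule for Tier 1.** Section 9.6.2: "Safety parameters or adverse events of special interest that are identified a priori constitute" Tier 1, which carries p-values and 95% intervals. The SAP summary in Section 9.1 says "P-values and confidence intervals for the incidence of AEs of clinical interest will be estimated using the Miettinen and Nurminen method".
- **Where the list is.** Section 9.6.2: "For this protocol, the specific Tier 1 adverse events are listed in" Table 7.
- **What Table 7 contains.** There are twelve Tier 1 rows. Eight concern the liver: one adverse-event row (*Hepatitis-related AEs*) and seven laboratory rows. Four concern muscle: CK at least 5xULN with muscle symptoms; CK at least 10xULN; the latter with symptoms; and the latter with symptoms judged drug-related.
- **Everything else.** Other terms and organ classes go to Tier 2 (interval, no p-value) or Tier 3 (descriptive only), according to a threshold of 4 participants.

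**The concern.** The protocol treats liver and muscle alike when it names its events of interest, but not when it lists what will be compared. For the liver, a clinically diagnosed event counts whatever the enzyme values. For muscle, a clinical event counts only when a CK threshold is also met. The documents do not define myopathy by a CK level, so the CK rows cannot be assumed to capture every myopathy an investigator records.

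Section 2.2.1 says myopathy increases with statin dose, especially in Chinese patients. The appended guideline lists myalgia among statin muscle reactions and among reactions when ezetimibe is combined with a statin (its Sections 10.1.1 and 10.1.2). Section 2.2.2 says there are no clinical data on the combination in Chinese patients. Safety and tolerability is the only secondary objective. A difference between arms in clinical muscle events, in either direction, could be spread over several terms and never be tested as one endpoint.

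**Working it through.** **1. The plan's own figure.** Section 9.6.2 justifies the Tier 2 threshold by saying that with equal arms and fewer than 4 events in each, the 95% interval for the difference always includes zero. This was checked at the extreme splits with the Miettinen-Nurminen score method and the arm sizes in Section 9.1 (180/2 = 90 per arm in Cohort A; 270/2 = 135 in Cohort B). At zero difference,

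z = (x1/n − x2/n) / sqrt[ p(1 − p) × (2/n) × 2n/(2n − 1) ], with p = (x1 + x2)/(2n).

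| Split | Per arm | 95% interval (points) | Two-sided p |
|---|---|---|---|
| 3 vs 0 | 90 | −0.85 to 9.4 | 0.082 |
| 3 vs 0 | 135 | −0.6 to 6.3 | 0.082 |
| 4 vs 0 | 90 | 0.2 to 10.9 | 0.044 |
| 4 vs 0 | 135 | 0.15 to 7.4 | 0.044 |

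The threshold reproduces. It also shows that a grouped muscle row could reach nominal significance from a 4 vs 0 split.

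**2. Tracing one event through Table 7.** Take a participant with a recorded myopathy or muscle-symptom adverse event and CK below 5xULN. The first muscle row fails on CK. The other three need at least 10xULN and fail too. The hepatic rows do not apply. The event is in no Tier 1 row. The same holds if no CK was taken around the event. After randomization the Schedule of Activities has chemistry, which includes CK (Table 9), only at Weeks 6 and 12; unscheduled and local tests are allowed.

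**3. What the fallback gives.** Outside Tier 1, each term and each organ class is tiered on its own count. The text of Section 9.6.2 puts an event in Tier 2 if **any** group has at least 4 participants; Table 7 says **all** groups. Read literally, a 7 vs 0 result fits neither Table 7 row, since it is not at least 4 in all groups and not below 4 in all groups. With a and b the binomial probabilities of at least 4 events in each arm, the chance of Tier 2 is 1 − (1 − a)(1 − b) under *any* and a × b under *all*. The event rates are assumptions:

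| Assumed rates | Cohort | Any group | All groups |
|---|---|---|---|
| 2% vs 8% | A | 94% | 10% |
| 2% vs 8% | B | 99.7% | 28% |
| 3% vs 6% | A | 85% | 23% |
| 3% vs 6% | B | 98% | 56% |

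Tier 2 gives an interval but no p-value under either wording.

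**4. Illustration of dispersal (assumed split).** In Cohort B, suppose one arm has 3 myalgia, 2 muscular weakness and 2 myopathy, in seven different participants, all outside the CK rows, and the other arm has none. Each term is below 4, so each is Tier 3 without an interval. As one endpoint:

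- p = 7/270 = 0.0259
- SE = sqrt(0.0259 × 0.9741 × 2/135 × 270/269) = 0.0194
- difference = 7/135 = 0.0519, or 5.2 points
- z = 0.0519/0.0194 = 2.68; two-sided p about 0.007

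If all seven are coded to one organ class, that class would get a Tier 2 interval under the *any* wording.

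**The case against.** Several counter-arguments have force.

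- **Muscle is in Tier 1.** A reader might infer that Table 7 leaves muscle events out. It does not: four rows concern muscle, and three of them require symptoms. What is absent is a row that does not depend on CK.
- **Biochemistry is part of the definition.** Section 4.2.1.2 speaks of muscle events that the scheduled blood tests are meant to detect, so CK-based rows are a natural reading of that sentence. Section 8.3, however, names muscular events without that link.
- **An event of clinical interest is not automatically Tier 1.** Section 8.4.7 is a reporting list. Overdose without symptoms is on it and has no Tier 1 row. One can argue that Table 7 is itself the a priori list. This stands as far as Section 8.4.7 alone goes. But the documents never separate events of interest, of special interest and of clinical interest, and Section 9.1 attaches p-values to the last of these.
- **CK may well be available.** Section 8 allows unscheduled samples and local laboratory use for safety, Section 4.2.1.2 also allows local testing for safety signals, and the discontinuation criteria in Section 7.1 presuppose repeat CK within a week. A missing CK is possible, not the rule. This does not help the event with a measured CK below 5xULN.
- **No comparison at all?** A reader might infer this too. The documents do not support it: such events are collected, reviewed clinically and given a Tier 2 interval if frequent enough. The 3 + 2 + 2 split is constructed.
- **Importance.** It is tempting to call muscle tolerability a main reason for the trial. The study rationale in Section 2.1 rests on LDL-C superiority only; Section 2.2.1 adds tolerability as a further remark, and safety has no formal hypothesis.

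**Conclusion.** The gap is real but narrow. The plan names muscle events as events of interest and promises inferential comparison for such events, yet following Table 7 literally gives no Tier 1 comparison to a muscle adverse event that lacks the required CK value. What is lost is one p-value and one guaranteed interval per cohort for clinical muscle events taken together. This rests on reading the three *of interest* phrases as overlapping, which the documents neither confirm nor exclude, and on myopathy not being defined by CK.

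The 7 vs 0 calculation shows what dispersal over terms could hide; it does not forecast the event count. The conflict between *any* and *all* in the Tier 2 rule is a separate inconsistency, but it makes the fallback for these events uncertain. The primary analysis, its power and its multiplicity control are untouched. The change should be made because it is cheap and restores the parallel with the liver.

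**What to change.** Add one Tier 1 row to Table 7, parallel to the hepatitis row: muscle-related adverse events, including myopathy and rhabdomyolysis, regardless of CK. Fix the preferred-term list before unblinding. Whether non-specific symptoms such as myalgia or weakness belong on it is a design choice to be stated then. Keep the four CK rows.

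If the restriction to CK-defined events is deliberate, Section 9.6.2 should say so, and Sections 4.2.1.2, 8.3, 8.4.7 and 9.1 should be worded to match. In either case the *any* and *all* wordings of the Tier 2 rule should be reconciled.

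Cost: Tier 1 goes from 12 to 13 rows per cohort, which adds one unadjusted nominal p-value in each. Section 9.6.2 already accepts such p-values without adjustment, so no alpha is spent. No new data are needed. The opening of Section 9 lets changes to non-confirmatory analyses made before unblinding be documented in the supplemental SAP.

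### Table 7 limits Tier 2 to adverse events with at least 4 participants in all treatment groups, while the text of section 9.6.2 says any treatment group

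*Combined protocol and SAP*

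**What the plan says.** The text of section 9.6.2 sets the rule for specific adverse events, system organ classes and predefined limits of change that are not Tier 1: "Membership in Tier 2 requires that at least 4 participants in any treatment group exhibit the event", and "all other adverse events and predefined limits of change will belong to Tier 3". Tier 2 receives point estimates with between-group 95% confidence intervals by the Miettinen and Nurminen method. Tier 3 receives point estimates by arm only.

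The text also explains why the threshold is 4: the interval for the difference "will always include zero when treatment groups of equal size each have less than 4 events".

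Table 7 in the same section defines the tiers for specific AEs and SOCs by two rows:

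- Tier 2: "incidence $\geq 4$ of participants in all of the treatment groups"
- Tier 3: "incidence $<4$ of participants in all of the treatment groups"

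Safety is analysed within cohort ("treatment groups will not be pooled across cohorts"), so each comparison has two arms.

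**The concern.** The text and the Tier 2 row cannot both be right. With two arms, an event falls into one of three patterns: both arms at 4 or more, both below 4, or split. The text puts the split pattern in Tier 2. The table's Tier 2 row excludes it, and so does the table's Tier 3 row, so the table alone assigns it no analysis.

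Split counts are the unbalanced ones, which the threshold was chosen to keep in view. Section 9.6.2 refers to Table 7 for the tiered approach, so output could be programmed from that row. Two analysts working from the same plan could then report different sets of intervals. Settling the rule after unblinding would be a data-dependent choice about which safety imbalances are shown with an interval. Safety and tolerability is the trial's only secondary objective (section 3).

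**Working it through.** **Inputs.** 180 participants in Cohort A and 270 in Cohort B, randomized 1:1 (sections 4.1 and 6.3.1), so n = 90 and n = 135 per arm, taking all randomized participants as treated. Interval method: Miettinen-Nurminen, 95% (section 9.6.2).

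**Step 1: set the rules side by side.**

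| Pattern (two arms) | Text of 9.6.2 | Table 7 |
|---|---|---|
| both ≥4 | Tier 2 | Tier 2 |
| one ≥4, other <4 | Tier 2 | neither row |
| both <4 | Tier 3 | Tier 3 |

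The rationale in the text justifies dropping the interval only when both arms are below 4. The table's Tier 3 row is the exact complement of the any-group rule. Only the Tier 2 cell disagrees.

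**Step 2: reproduce the plan's rationale.** With counts a and b in equal arms and p = (a+b)/(2n), the score statistic at zero difference is

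z = [(a−b)/n] / √[ p(1−p)·(2/n)·2n/(2n−1) ],

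and the 95% interval excludes zero when |z| > 1.96.

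- 3 v 0, n = 90: p = 3/180 = 0.01667; z = 0.03333/0.01914 = 1.74. For n = 135, z = 1.74.
- No pair with both counts at 3 or fewer excludes zero at either arm size. The plan's statement reproduces.

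**Step 3: apply the same test to split counts.**

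- 4 v 0, n = 90: p = 4/180 = 0.02222; z = 0.04444/0.02204 = 2.02. For n = 135, z = 2.01.
- 12 v 3, n = 90: z = 2.42. For n = 135: p = 15/270 = 0.05556; z = 0.06667/0.02793 = 2.39.

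Inverting the score statistic (constrained maximum likelihood, same variance factor) gives these intervals, in percentage points:

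| Counts | n = 90 | n = 135 |
|---|---|---|
| 3 v 0 | −0.85 to 9.37 | −0.59 to 6.34 |
| 4 v 0 | 0.24 to 10.90 | 0.15 to 7.38 |
| 12 v 3 | 2.13 to 19.03 | 1.35 to 12.97 |

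Against 0, 1, 2 or 3 events in one arm, the smallest count in the other arm whose interval excludes zero is 4, 7, 9 or 10, at both arm sizes. All of these are split counts.

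**Step 4: how often a count is split.** The plan gives no expected rates for specific AEs, so these are assumed. Let G be the binomial probability of 4 or more events in an arm. For independent arms, P(split) = G₁(1−G₀) + G₀(1−G₁). With equal rates this is 2G(1−G). At 2%, n = 90: G = 0.107, so 2 × 0.107 × 0.893 = 0.191. At 2%, n = 135: G = 0.285, so 2 × 0.285 × 0.715 = 0.408.

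| True rate, both arms | Split, n = 90 | Split, n = 135 | Split and interval excludes zero, n = 90 | Same, n = 135 |
|---|---|---|---|---|
| 1% | 2.6% | 9.0% | 1.0% | 2.5% |
| 2% | 19% | 41% | 3.6% | 4.5% |
| 3% | 41% | 49% | 4.4% | 4.3% |
| 10% | 3.3% | 0.1% | – | – |

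The upper end is a large true difference. Table 8 (section 9.9) gives 10.3 points as detectable at 80% power in Cohort A from a 1% control rate, that is 1% v 11.3%. With n = 90, G₀ = 0.013 and G₁ = 0.993, so P(split) = 0.993 × 0.987 + 0.013 × 0.007 = 0.98.

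**The case against.** The strongest reply is that the plan already settles the matter. The text of section 9.6.2 is a complete rule with a rationale that fits only the any-group reading, and the table's Tier 3 row agrees with it. Harm requires someone to follow one cell against all three. Table 7 is also abbreviated: it has no row for predefined limits of change outside Tier 1, although the text tiers these too, so it was not meant to be applied without the text.

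The figures can also be read as overstating the stakes. Most split counts at equal rates have an interval that includes zero, and those that exclude it at equal true rates are chance findings. The 98% uses a difference chosen for power, not an expected safety profile; section 2.2.2 describes comparable safety. The plan itself says the intervals "should be regarded as a helpful descriptive measure to be used in review, not a formal method". Tier 1 endpoints and the eight summary AE measures receive intervals whatever their counts. Section 9.1 adds that "Counts and percentages of AEs will be provided", so a 12 v 3 imbalance would still be visible.

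All of this stands as a limit on weight. It does not remove the contradiction: the Tier 2 cell states an operative classification rule that is wrong as written.

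**Conclusion.** The concern holds, as a minor one. Section 9.6.2 contradicts itself on Tier 2 membership, and the Tier 2 cell of Table 7 is the wrong statement. Read as a whole, the plan leaves no event unclassified, because the text is complete.

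If the cell were followed, split counts would lose their interval, including 4 v 0 and 12 v 3, where it excludes zero in both cohorts. How often this happens depends on assumed rates and independent binomial counts with 90 or 135 treated per arm. At equal rates of 1% to 3%, a split occurs in 2.6% to 49% of events, but a split with an interval excluding zero in only about 1% to 5%. The 98% at 1% v 11.3% is an extreme, not an expectation.

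No hypothesis, error rate or sample size depends on these intervals.

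**What to change.** In the Tier 2 row of Table 7, replace the all-groups condition with at least 4 participants in any treatment group, as in the text. The Tier 3 row can stay; it is then the exact complement.

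A cohort qualifier is not needed, because section 9.6.2 already keeps the cohorts separate. If one is wanted, it should go into both table rows and the sentence in the text, so that the wording stays aligned.

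The cost is one table cell and, compared with following the present cell, a few more descriptive intervals. Conduct, sample size and the primary analysis are unaffected. The correction should be made before unblinding.
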